7.3.2 Handling of Missing Efficacy Endpoints

For subjects who discontinue treatment (for any reason), subjects will continue to be followed and efficacy endpoints, data are collected where possible.

In situations where the efficacy endpoints are missing, all available data will be analyzed with a mixed-effects model for repeated measures (MMRM) as described in section $\underline{8.5.2.1}$. To evaluate robustness of results, sensitivity analyses will be performed with imputation methods for missing data as described in section $\underline{8.5.2.1.2}$.

7.4 Handling of Randomization Error (Part 2)

Eligible Part 2 patients will be randomized to either AXER-204 or to placebo. The randomization will be stratified based on pre-treatment American Spinal Injury Association Impairment Scale (AIS) grade (AIS A,B vs. AIS C,D) and prior receipt of study drug in Part 1 (Received AXER-204 in Part 1 vs. Did not receive AXER-204 in Part 1).

For patients who were classified differently based on AIS grade or prior receipt of study drug in Part 1 at pre-treatment compared to their stratified randomization assignment, any such inconsistencies will be documented as randomization errors and protocol deviations. In any such cases, pre-treatment value will be used in preference to the stratified randomization value for TFL reporting.

8. Statistical Methods

8.1 General Principles

- All data processing, summarization and analyses will be performed using SAS Environment / Version 9.4 (or later) of the SAS[®] statistical software package.
- The following principles will be applied to all TFLs unless otherwise stated:

Table 6 Statistical Analysis General Principles

Principle	Value
Significant tests	Two sided and use a 5% significance level
Treatment group labels and order	Part 1: AXER-204 xx mg
presented	Part 2: AXER-204 200 mg; Placebo
Tables	Data in summary tables presented by dose
	cohort/treatment group, assessment (where
	applicable), and visit (where applicable).

Principle	Value
Listings	All data collected presented by dose
	conort/treatment group, subject, and visit (where applicable) unless otherwise specified
Descriptive summary statistics for	Number of subjects (N), mean, standard deviation
continuous variables	(SD), median, minimum, maximum.
Descriptive summary statistics for categorical variables	Frequency counts and percentages [n (%)]
Denominator for percentages	Number of subjects in the analysis population, unless otherwise specified.
Include "Missing" as category	Yes, when the number missing is greater than zero for at least one dose cohort/treatment group.
Display for percentage	One decimal place, except for 100%
Display for 0 percentages	0
Display to one more decimal place than collected value	Mean, Median, Mean Difference
Display to two more decimal places than collected value	Standard Deviation
Limit of precision for displays	3 decimal places
Date Format	DDMMMYYYY
TFL orientation	Landscape
TFL output	For all tables and listings, 2.54 cm for the
	top/bottom/left/right margins and 8-point Courier New font

• For both safety and efficacy analysis, the baseline value will be defined as the last non-missing value before the first dose of study treatment.

8.2 Subject Disposition and Data Sets Analyzed

For Part 1, subject disposition will be listed and summarized by dose cohort and overall for the Safety population and will include the number and percentage of subjects that are included in each study population (Safety Population, FAS, PK analysis set, and ADA analysis set). For Part 2, subject will be listed and summarized by treatment group and overall for the All Randomized Set and will include the number and percentage of subjects included in each study population (Safety Population, mITT, PK analysis set, ADA analysis set, and PPS).

In addition, the number and percentage of subjects who complete the study and who discontinue early, including a breakdown of the primary reasons for discontinuation, will be presented.

8.3 **Protocol Deviations**

All protocol deviations for Part 1 will be listed.

For Part 2, Protocol deviation will be identified prior to database lock and unblinding. All protocol deviations will be listed. All important protocol deviations that impact the interpretation of efficacy outcome measures, leading to exclusion from the PPS, will be summarized by treatment group and overall for the mITT. Number and percentage of subjects with at least one important protocol deviations including a breakdown of type of protocol deviations will be summarized.

8.4 Demographics and Other Baseline Characteristics

8.4.1 Demographic and baseline characteristics

Demographic and baseline characteristics will be listed and summarized by dose cohort and overall for the Safety population. Standard descriptive statistics will be presented for the continuous variables of:

- Age (years);
- Weight (kg);
- Height (cm);
- Body mass index (BMI) (kg/m²);
- Time from injury (months), calculated as (date of the first dose of study treatment date of injury)/30.4375, date of injury will be obtained from the demographics eCRF page.

BMI recorded in pounds and inches will be re-calculated as the following: $BMI(kg/m^2) = BMI(lb/in^2) * 703$.

The total counts and percentages of subjects will be presented for the categorical variables of:

- Gender (Female, Male);
- Race (American Indian Or Alaska Native, Asian, African American, Native Hawaiian Or Other Pacific Islander, White, Other);
- Ethnicity (Hispanic or Latino, Not Hispanic or Latino, Unknown);
- Reproductive status (Fertile, Menopause, Sterilized, Unknown, Other);

- Injury ASIA Impairment Scale (A, B, C, D obtained from the ISNCSCI eCRF at screening;
- Neurological level of injury (C2, C3, C4, C5, C6, C7, C8, T1, T2), obtained from the ISNCSCI eCRF at screening;
- Cause of Spinal Cord Injury (Part 2 only) using the categories adopted by the National Spinal Cord Statistical Center.

Other baseline measurements, such as vital signs, will be summarized with the postbaseline measurements.

For Part 2, Demographic and baseline characteristics will be listed and summarized by treatment group and overall for the Safety population. The same list of demographic and baseline characteristics as those specified for Part 1 will be summarized by treatment group and overall. In addition, number and percentage of subjects who received study drug in Part 1 will be also summarized.

8.4.2 Medical History

Medical history will be coded using the Medical Dictionary for Regulatory Activities (MedDRA) [Version 22.0 (or a later version if updated during the study)].

All medical history will be listed, and the number and percentage of subjects with any medical history will be summarized for the Safety population by system organ class (SOC) and preferred term (PT) for each dose cohort for Part 1 (or for each treatment group for Part 2) and overall. Subjects with more than one medical history within a particular SOC are counted only once for that SOC. Similarly, subjects with more than one medical history within a particular PT are counted only once for that PT. Tables will be sorted in descending overall frequency by SOC, and then in descending overall frequency by PT within SOC, and then alphabetically.

8.4.3 Previous and Concomitant Medications

Medications received prior to or concomitantly with treatment will be coded by using the World Health Organization (WHO) Drug Dictionary [Version: Global B3-March 2019 (or a later version if updated during the study)] Anatomical Therapeutic Chemical (ATC) Classification codes.

Prior medications and concomitant medications are defined as follows:

- Prior medications are those with a start date and a stop date prior to the first dose date of study treatment;
- Concomitant medications are those with a start date on or after the first dose date of study treatment, or those with a start date before the first dose date of study treatment and a stop date on or after the first dose date of study treatment or ongoing at the end of study;

Statistical Analysis Plan

• New-onset medications are concomitant medications with a start date after the first dose of study treatment. New-onset medications are a subset of the full set of concomitant medications.

If a medication cannot be classified as "prior" or "concomitant" after applying imputation rules for missing/incomplete dates, it will be classified as concomitant.

Prior medications and concomitant medications will be listed together and summarized separately for the Safety population by dose cohort for Part 1 (or by treatment group for Part 2) and overall.

The number and percentage of subjects using any medication will be displayed together with the number and percentage of subjects using at least one medication within each therapeutic class (ATC-Level 2) and generic term. Tables will be sorted in descending overall frequency by the ATC level and in descending overall frequency by generic term, and then alphabetically.

8.5 Efficacy

8.5.1 Part 1

All efficacy data will be listed. The following efficacy endpoints will be summarized by dose cohort and overall, and by visit using standard descriptive statistics for the FAS, changes from baseline will be also summarized:

- ISNCSCI upper extremity motor total score, obtained from eCRF;
- ISNCSCI lower extremity motor total score, obtained from eCRF;
- ISNCSCI pin prick sensory total score, obtained from eCRF;
- ISNCSCI light touch sensory total score, obtained from eCRF;
- GRASSP strength total score, calculated as the sum of the total strength score for the right side and the total strength score for the left side;
- GRASSP sensation total score, calculated as the sum of the total sensation score for the right side and the total sensation score for the left side;
- GRASSP prehension ability total score, calculated as the sum of the total prehension ability score for the right side and the total prehension ability score for the left side;
- GRASSP prehension performance total score, calculated as the sum of the total prehension performance score for the right side and the total prehension performance score for the left side;
- SCIM III self-care total score, obtained from eCRF;
- SCIM III mobility total score, obtained from eCRF.

8.5.2 Part 2

8.5.2.1 Primary Efficacy Endpoint and Primary Efficacy Analysis

The primary efficacy endpoint is the change from baseline in bilateral UEMS to Study Day 169.

The null and alternative hypothesis for this endpoint are as follows:

 $H_0: \mu_A = \mu_P$

H_A: μ_A≠ μ_P

Where H_0 and H_A refer to the Null and alternative hypothesis to be tested, μ_A and μ_P refers to the mean change in bilateral UEMS from baseline to Study Day 169 for subjects randomized to AXER-204 and Placebo groups, respectively.

Primary analysis to compare the change from baseline in bilateral UEMS to Study Day 169 will be based upon a mixed-effects model for repeated measures (MMRM) using the mITT.

The MMRM model will include treatment (AXER-204 vs. Placebo), all post-baseline visits up until Study Day 169 (Study day 21, 63, 104, and 169), treatment-by-visit interaction, AIS grade (A, B vs C, D), and prior receipt of study drug in Part 1 (yes vs. no) as the fixed categorical effects, the baseline bilateral UEMS measurement as a covariate, and treatment-by-baseline UEMS interaction.

An unstructured covariance structure will be used to model the within-patient errors. If this analysis fails to converge, the following covariance structures will be tested in order, and the first covariance structure that converges will be used:

- toeplitz with heterogeneity (TOEPH)
- autoregressive with heterogeneity (ARH(1))
- compound symmetry with heterogeneous variances (CSH)
- toeplitz (TOEP)
- autoregressive (AR(1))
- compound symmetry without heterogeneous variances (CS)

The Kenward-Roger approximation will be used to estimate denominator degrees of freedom. Significance tests will be based on LS Means using Type III sum of squares.

Based on the MMRM, analysis of comparisons between treatment groups at each post-randomization visit will be performed. The primary analysis will be to compare

CONFIDENTIAL

treatment effect at Study Day 169. The adjusted means for each treatment group and the estimated treatment differences for the treatment comparisons will be presented for each post-randomization visit together with 95% confidence intervals for the differences and p-values for the treatment comparisons. The adjusted means and estimated treatment differences for the treatment comparisons will also be plotted, with corresponding 95% confidence intervals.

Descriptive statistics (number of subjects, mean, standard deviation, median, minimum and maximum) will be provided for baseline, post treatment and change from baseline by treatment group and visit.

8.5.2.1.1 Primary Efficacy Endpoint and Secondary Efficacy Analysis

A random coefficients model will be used to compare the rate of change (slope) in bilateral UEMS from start of study treatment until Study Day 169 between treatment group and control group. The model is similar to the MMRM model (section 8.5.2.1), except subject and subject by visit will be included as random effects. The unstructured covariance model will be used. If the computational algorithm fails to converge, the following covariance structures will be analyzed: TOEPH, ARH(1), CSH, TOEP, AR(1), CS. Reporting of model results will include the model estimate for the overall rate of change in bilateral UEMS and 95% CI, estimated treatment or control group rates and 95% CIs, and mean difference between treatment and control group along with the p-values. The adjusted means and estimated treatment differences for the treatment comparisons will also be plotted with corresponding 95% confidence intervals.

8.5.2.1.2 Sensitivity Analysis

Three sensitivity analyses will be performed for the primary efficacy endpoint.

• Multiple imputations assuming missing not at random (MNAR)

Sensitivity analysis will be performed using multiple imputations with unobserved data imputed prior to fitting the linear regression. An assumption of MNAR will be made based upon an approach using multiple imputations with missing data for all subjects imputed from a regression model estimated from patients in the placebo group who stay on until Study Day 169. The imputation model will include the randomization strata and the corresponding baseline value as predictor. The method of multiple imputations (MI) (Ratitch et al. 2013) using Pattern Mixture Model (Little and Wang 1996) will be used. The amount of non-monotone missing data is expected to be minimal and hence any non-monotone missing bilateral UEMS will be imputed using the Markov Chain Monte-Carlo method. SAS PROC MI

and MIANALYZE will be used to generate 100 complete datasets and combine the results from each complete dataset analyzed using the same MMRM model as described above in section 8.5.2.1.

• Multiple imputations assuming missing at random (MAR)

An assumption of Missing at Random (MAR) will be made and subject's missing bilateral UEMS data will be imputed using those with available data within the treatment group they were assigned to using an approach similar to above as described in section 8.5.2.1.

• Excluding patients with important protocol deviations and who did not receive 80% of the planned treatment

An analysis excluding patients with deviations that may affect the efficacy of the study treatment will be conducted in per protocol set. The same MMRM method as the primary analysis as described in section 8.5.2.1 will be used. This analysis will use the principal stratum strategy, to assess the sensitivity of the results to the occurrence of the intercurrent events like important protocol deviations prior to assessment scheduled on Study Day 169 and not receiving at least 5 doses (~80%) of the planned cumulative number of doses of treatment as described in section 3.1.2.1.6.

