## 15. STATISTICS

## 15.1. Sample Size

The Part 1 sample size was derived empirically from experience with previous single ascending dose clinical studies in other disorders and is deemed appropriate to achieve the study objectives.

The Part 2 sample size was selected to ensure adequate power for detecting treatment-related change in bilateral UEMS (Score from 0 to 50).

A 5-point difference, between the treated and placebo groups, in the change from baseline to 6 months in bilateral UEMS is considered clinically meaningful. Analysis of historical data for cervical SCI patients for the period between ~6-12 months following acute SCI indicates a standard deviation of bilateral UEMS change over 6 months to be around 3 to 4 points.

With a sample size of 12 subjects per active and placebo group, Part 2 of the study has 80% power with Type I error of  $\alpha$ =0.05 (two sided), assuming a 5-point difference as indicated above, and with a common standard deviation within each treatment group of approximately 4 in the change from baseline to 6 months in bilateral UEMS.

Accounting for uncertainties in the assumptions based upon historical data used to extrapolate for estimating the sample size in this study and the need for estimation of missing data a sample size of approximately 16 subjects per treatment arm (32 total) will be randomized.

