Study participation for each subject in Part 1 is expected to be up to 16 weeks in duration, with up to an 84-day screening period, a 3-day in-clinic treatment period, and a follow-up period through 29 days post-dose:

 Screening (up to 84 days prior to Study Day 1). Subjects have 84 days from the time of signing informed consent to complete their screening assessments and, if needed, their washout period for prohibited concomitant medications. However, clinical laboratory tests required for screening must be completed within 28 days prior to Study Day 1.

- Treatment period: Check-in Day 1, administration of study drug, 3-night inclinic stay, and discharge on Day 4 following the completion of all scheduled procedures.
- Follow-up: Subjects will have follow-up visits for up to 29 days post-dose as follows: subjects will receive a phone call on Study Days 5, 6 and 7 to inquire about their general health and will return to the clinic for visits on Study Day 8 (± 1 day), Study Day 15 (±3 days) and Study Day 29 or Early Termination (ET) (± 4 days).

2.2.2 Part 2

Part 2 is a multicenter, randomized, double-blind, placebo-controlled, repeat dose study in CSCI subjects. Approximately 32 subjects will be randomized (ratio 1:1) to receive AXER-204 or placebo (an isotonic phosphate buffered saline formulation). Subject to review of the safety, tolerability, and pharmacokinetic data from Part 1 and DSMB approval, the dose will be 200 mg given once every 3 weeks for 15 weeks as outlined in the schedule of events. Subject to DSMB approval, the dose may be reduced to 90 mg and the dose interval may be modified based on data from Part 1 but is not expected to be less than once every 14 days or more than 28 days. Subject to DSMB approval, the dose and dose frequency may also be adjusted during Part 2 based on emergent safety and tolerability data.

Study participation for each subject in Part 2 is expected to be up to 337 days in duration, with up to an 84-day screening period, a 104-day treatment period, and then post treatment follow-ups at Study Days 137, 169, and 253:

- Screening (within 84 days prior to Day 1). Subjects have 84 days from the time of signing informed consent to complete their screening assessments and, if needed, their washout period for prohibited concomitant medications. The screening laboratory tests must be completed within 28 days prior to Study Day 1.

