2.3 Sample Size

2.3.1 Part 1

The Part 1 sample size of 24 (6 subjects per dose) was derived empirically from experience with previous single ascending dose clinical studies in other disorders and is deemed appropriate to achieve the study objectives, with adequate exposure to assess safety for dose selection in Part 2.

2.3.2 Part 2

The Part 2 sample size of approximately 32 subjects was selected with the goal of ensuring adequate power for detecting meaningful treatment-related change in bilateral Upper Extremity Motor Score, UEMS (Score from 0 to 50). Little or no spontaneous improvement in motor score is expected in people with chronic SCI, more than one year from injury (i.e. $\Delta UEMS = 0$) (Fawcett et al. 2007). As shown in Table 1, we have targeted detection of 5-point improvement in UEMS (and possibly less) as functionally relevant in the chronic cervical SCI patients recruited to this study. The potential impact of missing data and a correction for non-normal distribution of the data are not included in these estimates.

Table 1	Estimated power as a function of enrollment, effect size, and
normal v	riability of the outcome measure (Δ UEMS)

	∆ UEMS = 5		∆ UEMS = 4		∆ UEMS = 3	
Enrollment	nt SD = 3 SD = 4		SD = 3	SD = 4	SD = 3	SD = 4
32	99%	96%	95%	78%	78%	53%
26	98%	92%	90%	68%	68%	45%
20	94%	85%	80%	56%	56%	35%

SD = Standard deviation of the change in UEMS

Based on 2 sided α = 0.05 using NQuery (Version 4.0).

 Δ UEMS: A smaller improvement in Δ UEMS (e.g. 2 points) could be clinically meaningful if it occurred in a muscle group essential for a particular activity of daily living such as grasping in the chronic SCI population. A 3-point improvement in

CONFIDENTIAL

Statistical Analysis Plan ReNetX Bio, Inc

UEMS has been identified as the minimum clinically important difference in acute cervical SCI patients (Scivoletto et al. 2013). Although a minimum clinically important difference in UEMS has not been determined for chronic SCI patients, chronic SCI patients may have greater awareness of personal benefit resulting from changes due to their stable baseline function (Wu et al. 2015).

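### SAP 8.5.2.1.2 names strata and baseline, but no interim UEMS visit, as imputation predictors; read literally, the MAR sensitivity analysis assumes more than the MMRM it is meant to check

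*SAP*

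**What the plan says.** SAP 7.3.2 analyses all available data with the MMRM and presents the imputation analyses as a check on robustness. SAP 8.5.2.1 fits that MMRM to change in UEMS at Days 21, 63, 104 and 169 with an unstructured within-patient covariance. A subject who leaves after Day 104 therefore still informs the Day 169 estimate through three earlier values.

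SAP 8.5.2.1.2 then describes two imputation analyses.

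- **MNAR.** Missing values in both arms come from a regression estimated in placebo subjects who reach Day 169. On predictors it says: "The imputation model will include the randomization strata and the corresponding baseline value as predictor". Intermittent gaps are filled by MCMC, with no variable list. Each of 100 completed data sets is analysed with the primary MMRM.
- **MAR.** Here a "subject's missing bilateral UEMS data will be imputed using those with available data within the treatment group they were assigned to". No predictors are listed. The bullet refers back to the preceding approach and cites 8.5.2.1, which is the MMRM section and contains no imputation model.

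SAP 8.5.2.2.1 carries the same methods to GRASSP prehension performance and SCIM III self-care. No dropout rate is given; of its power table, SAP 2.3.2 says that "The potential impact of missing data and a correction for non-normal distribution of the data are not included in these estimates".

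**The concern.** The only predictors named are the strata and baseline, and the only imputation method that the MAR bullet can be pointing back to is the one just above it. A programmer following the text literally would leave Days 21, 63 and 104 out of both imputation models.

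For the MAR analysis this changes the assumption. The MMRM needs missingness at Day 169 to be ignorable given arm, strata, baseline and the earlier UEMS values. Imputation from strata and baseline needs it to be ignorable without the earlier values, which is a stronger requirement. Fitting the MMRM afterwards does little to repair this, because the Day 169 cell has already been filled without regard to the subject's own course. If dropout follows early response, the sensitivity analysis could disagree with the primary for that technical reason alone, or agree by accident.

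**Working it through.** **1. The plan's own figure.** Protocol 15.1 states "With a sample size of 12 subjects per active and placebo group, Part 2 of the study has 80% power", for a difference of 5 and SD of about 4; SAP 8.1 sets a two-sided 5% level.

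n per arm = 2(z₀.₉₇₅ + z₀.₈₀)² σ²/δ² = 2 × (1.960 + 0.842)² × 16/25 = 10.05, so 11 by the normal approximation. The noncentral t gives power of 79.6% at 11 and 83.3% at 12. The stated 12 is reproduced. The planned 16 per arm, difference 5 and SD 4 are used below.

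**2. Assumptions.** The documents give neither a dropout rate nor a between-visit correlation. Ranges are used: 10% and 20% dropout, or 2 and 4 dropouts per arm, and AR(1) correlation from 0.5 to 0.9.

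**3. Size of the MAR effect by hand.** Let f be the fraction missing in an arm, β the slope of Day 169 change on Day 104 change, and d the gap in mean Day 104 change between completers and dropouts. Without Day 104 as a predictor, dropouts are given roughly the completers' mean, so

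- error in an arm mean ≈ f × β × d
- error in the treatment difference ≈ f_A β d_A − f_P β d_P

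The second line is zero when dropout has the same pattern in both arms. If only active-arm dropout is selective, with β taken as the correlation and d assumed to be 4 to 5 points (1 to 1.25 SD):

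- 2 of 16 leave, β = 0.5: 0.125 × 0.5 × 4 = 0.25, to 0.125 × 0.5 × 5 = 0.31
- 4 of 16 leave, β = 0.85: 0.25 × 0.85 × 4 = 0.85, to 0.25 × 0.85 × 5 = 1.06

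**4. Simulated bias in the treatment difference, MAR imputation.** Two simulations were run at 16 per arm and SD 4. Simulation A used conditional-mean imputation, a true difference of 5 and 3,000 runs. Simulation B used proper multiple imputation with 2 or 4 dropouts per arm and correlation 0.5 to 0.85.

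| Dropout pattern | Strata + baseline | Interim UEMS added |
|---|---|---|
| Random, or tied to Day 104 equally in both arms (A and B) | none material | none material |
| Tied to Day 104 in the active arm only (A) | +0.15 to +0.4 | about 0 |
| Tied to Day 104 in the active arm only (B) | +0.3 to +1.1 | within about 0.1 of 0 |
| Opposite directions by arm, an extreme case (A) | +0.3 to +1.2 | about 0 |

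In B the added predictor was Day 104; in A it was all three visits. The MMRM-like estimate in A also stayed at about 5.0 throughout.

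**5. Precision at 20% random dropout (SD of the estimated difference, simulation A).**

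| Correlation | MMRM-like | MAR, strata + baseline | MAR, plus Days 21, 63, 104 |
|---|---|---|---|
| 0.5 | 1.66 | 1.71 | 1.77 |
| 0.8 | 1.55 | 1.67 | 1.60 |
| 0.9 | 1.51 | 1.71 | 1.53 |

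Baseline-only MAR imputation is 3% (1.71/1.66) to 13% (1.71/1.51) more variable than the MMRM. Entering all three visits within arm is worse still at correlation 0.5. In simulation B the mean Rubin standard error there, with 4 random dropouts per arm, rose from 1.84 to 2.11.

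**6. Placebo-based (MNAR) analysis at 20% random dropout.** If dropouts receive the placebo mean, the expected estimate is 5 × (1 − 0.2) = 4.0; simulation A gave 3.96 to 3.98. With interim values as predictors it gave 4.34 to 4.63. Omitting them therefore adds about 0.4 to 0.65 points to the pull toward zero. The SD of the baseline-only version was 1.43 to 1.46, below the MMRM-like 1.51 to 1.66.

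**The case against.** The strongest reply is that the SAP does not exclude the interim visits. It says what the model will include, not that nothing else enters. Separating monotone from non-monotone gaps, and invoking a pattern-mixture method, makes most sense if several visits are imputed in sequence. The MAR bullet names no predictors at all, and the section it cites lists all four visits. This stands: the defect is an under-specified model with a literal reading that omits the interim data, not a stated rule to ignore them. That both analyses are baseline-only is an inference.

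A reader might also infer that the sensitivity analyses are biased in general. The calculations do not support that. Error in one arm's mean is not error in the between-arm difference that SAP 3.1.2.1.5 defines. When 2 to 4 dropouts per arm were tied to Day 104 in the same way in both arms, arm means were off by 0.2 to 1.4 points but the difference stayed within about 0.1 of zero.

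Nor can one say that both analyses are noisier than the MMRM. That holds modestly for MAR and fails for the placebo-based analysis. In the MNAR analysis, movement toward placebo is the purpose, so departure from the primary is not itself bias.

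Finally, adding predictors has a price. An intercept, two strata, baseline and three visits make seven parameters per arm, fitted to 12 to 14 completers (16 less 2 to 4). This also stands and shapes the fix.

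**Conclusion.** The point holds as an under-specification with a consequence for the MAR check. Followed literally, that analysis rests on a stronger assumption than the primary MMRM, and its treatment difference can be off by about 0.3 to 1.1 UEMS points when dropout depends on Day 104 UEMS in the active arm only. Simulation A gave 0.15 to 0.4 under its own dropout settings. The size turns on how many leave and how closely leaving follows the Day 104 score, which the documents do not fix. Under random or arm-symmetric dropout there is no material bias. For comparison, SAP 2.3.2 cites 3 points as the minimum clinically important difference in acute cervical injury.

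For the MNAR analysis the choice only sets how severe the stress test is, by about 0.4 to 0.65 points at 20% random dropout, and should be stated for that reason. The primary MMRM is unaffected. The documents do not show which predictors were actually programmed.

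**What to change.** In SAP 8.5.2.1.2, state that imputation proceeds visit by visit. Predictors are the strata, baseline UEMS and the preceding observed or imputed UEMS, at minimum the most recent visit. Models are fitted within arm for MAR and in placebo for MNAR. Replace the MAR reference to 8.5.2.1 with a reference to this imputation model. Apply the same to GRASSP prehension performance and SCIM III self-care with their own visits, which Protocol Table 6 gives as Days 63 and 104 before Day 169. The MNAR bullet also mentions both a linear regression and the MMRM as the model for the imputed data; the same edit can settle which is meant.

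The cost is a few sentences and a small change to the imputation step. The statistical downside is some loss of precision at low visit correlation if all three earlier visits are entered; using only the latest visit largely avoids it.

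SAP section 10 records that the Day 169 data were unblinded and analysed before its changes were made. If the predictors already used match this description, record them in a dated clarification. If not, report the new version alongside the analysis already run, labelled as post-unblinding.
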